## Background and Significance

Orthognathic surgery is an essential part of correcting dentofacial deformities. The most common surgery for correcting mandibular deformities is the bilateral sagittal split osteotomy (BSSO). The BSSO was first developed in 1957 by Obwegeser(1), and allowed for anteroposterior correction of the mandible in either a Class II or Class III direction. The BSSO has been modified over time to improve surgical stability and reduce negative post-operative sequelae. Despite the modifications, there are still several potential complications that patients may experience. The most common post-operative complications are pain, swelling and nerve dysfunction.

As with any surgery, pain and swelling are unavoidable, but the extent can be variable. A variety of both pharmaceutical and non-pharmaceutical approaches are generally used to improve pain and swelling, including warm compresses, pressure dressings and analgesics. Physical interventions may reduce swelling, which in turn reduces pain, but are limited in their penetration. Meanwhile medications carry their own potential negative consequences; opioids carry a risk for dependence and neutropenia and non-steroidal anti-inflammatories can cause digestive issues, renal problems.

Nerve dysfunction leading to neurosensory deficits are a relatively common side effect of a BSSO, with literature estimating rates between 9% to 84.6% (2, 3) The inferior alveolar nerve (IAN) runs through the mandibular canal in the body of the mandible, with a branch, the mental nerve, splitting off and exiting the bone at the mental foramen between the first and second premolars. The IAN provides sensation to the gingiva and teeth, while the mental nerve provides sensation to the lips and the chin. During the BSSO, the IAN is necessarily moved and is at risk for either direct or indirect injury, which leads to the neurosensory deficits which are usually transient, but can be permanent in some cases (4-7). Therapy for IAN dysfunction is limited.

One treatment modality that has solid evidence to treat both sensory nerve dysfunction and pain is low-level laser therapy (LLLT). LLLT has been established as viable therapy that modulates the body's own healing potential in recovery from injury and surgery. The proposed mechanism of LLLT is that low intensity laser light applied to body tissues penetrates and scatters into the tissue, and the scattered energy stimulates a cascade reaction that leads to upregulating of healing and a reduction of inflammation (8).

Existing studies have shown that LLLT can modulate the post-surgical healing and pain (9, 10) and nerve recovery in orthognathic surgery patients (11-15.). Two systematic reviews have also determined that LLLT is an efficacious therapy to reduce pain and have significant long-term improvement neurosensory deficits over placebo (16, 17). Additionally, the literature has a consensus that the adverse effects of LLLT are virtually non-existent, with both review papers noting no negative complications reported in any of the papers included in the reviews. Both review papers, however, discuss that the existing literature has too few studies that are well-designed. Both review articles recommended more objective analysis of neurosensory function, as many relied on objective patient reports, and a longer follow-up period. Additionally, many studies have been conducted using a split-mouth design, in which one side receives LLLT and the other side doesn't, in order to increase the sample size without increasing the number of patients. The issue is, according to the current understanding of LLLT (8, 9), the photobiomodulation effect can travel away from the site of LLLT administration. There are no documented adverse effects of LLLT.

This study would aim to study the effects of LLLT on pain, swelling and neurosensory function on patients who have undergone orthognathic surgery with BSSO and compare the effects on a control group of patients undergoing similar surgery who will not receive any extraordinary post-op care.

### **Hypothesis**

Administration of low-level laser therapy along the skin over the mandibular body of patients who have had bilateral sagittal split osteotomy surgery for correction of the position of the mandible will reduce pain and swelling and improve neurosensory dysfunction when compared to patients who do not receive the laser treatment.

### **Study Design**

The study will have two groups into which patients will be assigned to a control group and an experimental group through a random number generator. Patients will undergo their planned surgical procedure and receive instructions as per standard clinic protocols, in both pre- and post-operative settings. The standard instructions include information on pain and swelling management. The patients will also receive post-operative medications, including an NSAID and an opioid for pain management and a steroid to reduce inflammation and swelling. The patients will be seen at one-week intervals for six weeks for post-operative follow-ups, as per standard clinic protocols. The experimental group will undergo low level laser therapy (LLLT) at weekly intervals. Subject treatment assignments will remain blinded until the final subject has completed follow up and all data has been recorded and validated. Urgent, immediate unblinding due to medical emergency may be authorized by the Investigator. When possible, the treatment assignment will be provided to the treating physician in order to maintain the blind for the Investigator and study staff. All instances of subject unblinding will be documented in the study record.

The proposed LLLT protocol will use the Biolase Epic X, an InGaAsP diode laser (940nm) using the pain relief handpiece, a device which has received FDA approval (GUDID 00647529002537) for the treatment of pain, muscle relaxation and healing via increased local circulation. The LLLT will be administered to the experimental group at 30 j/cm^2. The laser will be applied extraorally, on the skin overlying the mandible. Application will be for 40 seconds per side, with 10 seconds administered in four places along the jawline, 1 cm apart starting from the gonial angle. The timing would coincide with standard post-operative care, with the first LLLT administration performed on post-operative day 1, prior to the patient's discharge from the hospital. The follow-up LLLT doses would be given at the standard post-op follow-up visits, at one-week intervals, which would be at week 1, week 2, week 3, week 4, week 5, and week 6. Patients will be seen for evaluation at week 8 and again at approximately 20 weeks post-surgery. The control group will follow the same post-op visit schedule, but receive a dummy treatment in which the laser handpiece is moved over the patient's jaw in a similar fashion as the experimental but without laser irradiation.

Nerve function, pain and swelling will be measured according to objective measures. A baseline measurement will be recorded pre-operatively for nerve function and pain. Baseline for swelling will be used from the final measurement at week 8, due to the changes in mandible length caused by the orthognathic surgery. Measurements for each outcome will also be performed on the days for which

LLLT is administered. The individual who performs the assessment will be blinded to the group to which each patient belongs.

To evaluate nerve function, three tests will be conducted, a two-point discrimination (TPD) test, a hard stimulus test and soft stimulus test. For the TPD test, the patient will be instructed to close their eyes, and a caliper will be placed on the lateral aspect of the patient's chin. The calipers will start at 0 mm and be incrementally opened in .5mm increments, and the first distance felt by the patient as two distinct points will be recorded reported in millimeters. For the soft- and hard- stimuli tests, the lower face will be divided into eight regions, with four symmetric regions per side. Region 1 will be from the skin on the chin at the midsagittal plane laterally 1 cm. Region 2 will be the skin from the edge of Region 1 extending laterally 1 cm. Region 3 will be the skin from the edge of Region 2 extending laterally 1 cm. Region 4 will be the vermillion of the lower from the midsagittal plane to the commissure. The regions will be designated by an "L" for left or "R" for right, plus a number as per the above scheme. Each region will be checked for nerve function via two tests, a cotton-swab test and a two test. During the evaluation, the patient will be instructed to keep their eyes closed. The cotton-swab test will involve the skin in each region being lightly brushed in a 2cm vertical path twice per region, and the patient reporting if they feel the contact. Likewise, the toothpick test will involve the skin being slightly depressed by the edge of a toothpick in three spots separated by 1 cm each per region, and the patient reporting if they feel the contact. The responses will be recorded as positive or negative for soft (swab) or hard pressure (toothpick), by region.

Pain will be reported via use of a visual analogue scale (VAS). The patient will rate the intensity of the pain on each side of the mandible at each visit. The intensity of the pain will be from zero, meaning complete absence of pain, to 10, indicating the maximum amount of pain imaginable.

Swelling will be measured with a soft measuring tape from the tip of the chin to the lower lobe of the ear, bilaterally. The calculation of the swelling index will be done by subtracting the baseline length (from the six-week post-operative visit) to the measured length and dividing the difference by baseline length and multiplying by 100.

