### **Outcomes (primary and secondary)**

In this study, the predictor variable was the use of laser therapy versus placebo treatment after orthognathic surgery on the mandible. The primary outcome variable was neurosensory disturbance recovery by the TPD, hard and soft sensory tests. The secondary outcome variables are pain reduction, as measured by change in VAS, and swelling reduction, as measured by soft-ruler measurement of lower face.

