### Participant Recruitment

The patient pool for this study will be drawn from regular patients scheduled to undergo orthognathic surgery at Jacobi Medical Center. Patients who have been cleared for orthognathic surgery already must be in good health and understand the risks of the surgery. The only additional requirements for inclusion are 1) the planned surgery includes bilateral sagittal split osteotomies; 2) patients must be free from pre-operative inferior alveolar neurosensory deficiencies; 3) the patient cannot have an intra-operative

accidental fracture or rupture of the inferior alveolar nerve. The details of the whole orthognathic surgery will be recorded (including maxillary procedure, genioplasty, and direction of positional change of the mandible) but will not alter eligibility for enrolment in the study.

Since 2013, over 30% of the patients treated for orthognathic surgery at Jacobi Medical Center are between the ages of 15 and 18, which is in line with orthognathic surgery in general. As such, the study aims to include these patients in the potential pool of subjects. Because of the significant portion of patients under the age of 18 in general, and their inclusion will allow for age to be examined as a related factor in how healing proceeds. Their inclusion will also allow for an adequate sample size.

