### **Data analysis**

The primary outcome, change in neurosensory deficit, is measured by the three clinical tests, TPD, soft-stimulus and hard-stimulus. For TPD, the difference between the LLLT group and placebo group at each time point will be compared using an independent t-test, with alpha set at .05. The soft- and hard-stimulus tests for each region will be analyzed at each time point with a chi-square test. VAS pain score and swelling index will be analyzed using independent t-tests for the measurements on each side at each time point, with alpha set at .05. Linear regression will be performed to analyze the relationship of the pain, swelling and nerve tests with age, skeletal class, direction and magnitude of mandibular movement, and inclusion of genioplasty.

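### No nerve or pain score is assured between surgery and the first laser session, so the day-1 test is ambiguous and a useful covariate is given up

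*Combined protocol and SAP*

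**What the plan says.** Study Design sets the reference for two of the three outcomes: "A baseline measurement will be recorded pre-operatively for nerve function and pain". Participant Recruitment adds that "patients must be free from pre-operative inferior alveolar neurosensory deficiencies", so the nerve baseline is normal by design.

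Treatment starts soon after surgery, "with the first LLLT administration performed on post-operative day 1, prior to the patient's discharge from the hospital", and continues weekly to week 6. On the timing of assessments, Study Design says "Measurements for each outcome will also be performed on the days for which" the laser is given. It does not say whether an assessment comes before or after the laser or dummy on the same day. Evaluations at week 8 and about week 20 follow, with no laser.

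The outcome wording implies movement from a starting point. Outcomes states: "The primary outcome variable was neurosensory disturbance recovery by the TPD, hard and soft sensory tests". The pain outcome is "pain reduction, as measured by change in VAS". Data analysis states: "The primary outcome, change in neurosensory deficit, is measured by the three clinical tests, TPD, soft-stimulus and hard-stimulus". None of these sections names the time from which recovery or change is counted.

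Data analysis compares the arms at every measured visit with unadjusted independent t-tests for TPD and VAS. The planned regression covers age, skeletal class, mandibular movement and genioplasty. It lists no initial-deficit score.

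**The concern.** Surgery causes the disturbance from which patients are meant to recover. A score taken before surgery, in patients selected to be normal, carries little information on how badly the nerve was affected. The natural measure of that is a score taken after surgery and before any laser. Day 1 could supply it, but only if the assessment comes first, and the plan does not ensure this.

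Two things follow. The day-1 comparison cannot be interpreted as written, because it is either a check of chance differences or a test of one laser session. In addition, a probable predictor of later sensation and pain is not secured for the analysis, in a trial of only 23 per arm. If the order is neither fixed nor recorded, it cannot be reconstructed after enrolment.

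**Working it through.** **1. The schedule set out in order** (Study Design; Participant Recruitment)

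| Measurement | After surgery? | Laser that day? | Order stated? |
|---|---|---|---|
| Pre-operative | No | No | Not needed |
| Day 1 | Yes | Yes, first session | No |
| Weeks 1 to 6 | Yes | Yes | No |
| Week 8, about week 20 | Yes | No | Not needed |

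In the laser arm, the number of post-surgical measurements assured to precede the first session is 0. In the dummy arm the day-1 score is laser-free in either order, so the uncertainty concerns the laser arm only.

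**2. What the day-1 test means under each order**

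- Assessed before: neither arm has yet received anything different, so any difference is chance and the test says nothing about efficacy.
- Assessed after: the test may reflect one session, and the laser arm has no untreated post-surgical score. Day 1 would then be a poor covariate, because adjusting for it could remove part of the treatment effect.

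The order must therefore be fixed before day 1 can be used for adjustment.

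**3. The plan's sample size, reproduced**

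Inputs from Sample Size: difference 0.5, SD 0.5, power 90%. Alpha is 0.05 from Data analysis; two-sided is assumed. The standardised difference is 0.5/0.5 = 1.0. The exact two-sample t-test needs 22.02 per arm, which matches the plan's figure of just over 22, rounded up to 23. Power at 23 per arm is 91.2%. None of this depends on the baseline, so the stated number need not change.

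**4. Precision available from a pre-laser day-1 score**

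The documents give no correlation r between day-1 and later scores, so r = 0.3 to 0.7 is an assumption. An ANCOVA covariate removes a fraction r² of residual variance and leaves SD × √(1 − r²). Raw change from day 1 has SD × √(2(1 − r)), taking equal variances at the two times. Both columns use 23 per arm and the planned difference of 0.5. The single degree of freedom spent on the covariate is ignored.

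| r | Variance removed (r²) | ANCOVA SD | ANCOVA power | Change SD | Change power |
|---|---|---|---|---|---|
| 0 | 0% | 0.500 | 91.2% | 0.707 | 65% |
| 0.3 | 9% | 0.477 | 93.5% | 0.592 | 80% |
| 0.5 | 25% | 0.433 | 96.9% | 0.500 | 91.2% |
| 0.7 | 49% | 0.357 | 99.6% | 0.387 | 99.0% |

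In this range ANCOVA never does worse than the planned test. Raw change does worse whenever r is below 0.5.

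**The case against.** The strongest reply is that the primary comparison is sound as it stands. Patients are randomised, the control arm receives a dummy application, the assessor is blinded, and the arms are compared directly. That stands. A reader might infer that the trial cannot separate a laser effect from chance imbalance in nerve injury. The documents do not support this. With 23 per arm the standard error of a baseline difference is √(2/23) = 0.295 SD, so a difference of at least 0.3 SD (z = 0.3/0.295 = 1.017) arises in about 31% of trials. This holds for any covariate at this size, and the t-test's standard error and the 5% alpha already allow for it.

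Some other readings also go too far:

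- **That there is no untreated reference at all.** The pre-operative score is untreated and is each patient's own normal, so it is a valid reference for return to normal.
- **That only a known fraction of patients can recover.** Background cites deficit rates of 9% to 84.6%, which would be about 4 to 39 of 46 (46 × 0.09 = 4.1; 46 × 0.846 = 38.9). The protocol attaches no time point or test definition to those rates, so they cannot be turned into a count for this trial.
- **That sites would differ in order.** The protocol names one clinic. Only variation between visits or assessors is possible.
- **That assessing after the laser would unblind the assessor.** Nothing in the documents supports this; they report no known adverse effects of the laser.
- **That the pain analysis measures the wrong thing.** Data analysis compares VAS scores between arms at each visit, which does address whether the laser arm has less pain. What remains is that the change named in Outcomes has no stated reference.

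It can also be said that day 1 is a poor severity measure. In part this stands. Swelling, residual anaesthetic and the post-operative analgesics and steroid may all affect it, and Study Design gives no TPD value for a patient who never feels two points. These limit the gain from adjustment. They do not explain leaving the order unstated.

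**Conclusion.** The point holds as a matter of clarity and precision, not of bias. The plan does not assure a post-surgical, pre-laser score for nerve function or pain, and it tests day 1 without saying what that test represents. The text of the plan is enough to establish both.

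The size of the precision loss is conditional. At an assumed correlation of 0.3 to 0.7, adjustment would remove about 9% to 49% of residual variance. It would raise power from 91.2% to between 93.5% and 99.6%, if the planned difference of 0.5 and SD of 0.5 hold. If day-1 scores are heavily distorted, the gain falls towards zero.

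A reader might conclude that recovery should be redefined as raw change from day 1. The working does not support that: at correlations of 0 to 0.3, power would fall to about 65% to 80%. This is a cheap improvement worth making before enrolment, and it does not invalidate the planned comparison.

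**What to change.** In Study Design, state that all outcome measurements are completed before the laser or dummy is applied at every treatment visit, including day 1.

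In Data analysis:

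- Compare TPD and VAS at visits after day 1 by ANCOVA, with the day-1 pre-application score of the same measure as covariate.
- Report day 1 as a description of post-surgical status in each arm, not as an efficacy test.
- Keep the pre-operative score as the reference for return to normal, and say so where recovery and change are defined.
- Do not replace the between-arm comparison with raw change from day 1.

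The cost is protocol wording and a fixed order within visits that already exist. No visit, test or patient is added, and the sample size stays at 23 per arm. The downside is small: the covariate is imperfect, for the reasons given under the objection, and the gain may be modest.

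### The swelling index is referenced to a post-treatment reading taken at most two weeks after the last laser session; any between-arm difference remaining then is subtracted from every other visit

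*Combined protocol and SAP*

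**What the plan says.** All of this is in the combined protocol and SAP.

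- **Treatment times (Study Design).** Laser or dummy treatment is given on post-operative day 1 and then at follow-up visits, "which would be at week 1, week 2, week 3, week 4, week 5, and week 6". That makes seven sessions, the last at week 6.
- **Later visits (Study Design).** "Patients will be seen for evaluation at week 8 and again at approximately 20 weeks post-surgery".
- **Reference for swelling (Study Design).** "Baseline for swelling will be used from the final measurement at week 8". The reason given is "due to the changes in mandible length caused by the orthognathic surgery". The pre-operative baseline covers the other outcomes only: "A baseline measurement will be recorded pre-operatively for nerve function and pain".
- **Index (Study Design, swelling paragraph).** It is formed by "subtracting the baseline length (from the six-week post-operative visit) to the measured length", then "dividing the difference by baseline length and multiplying by 100". The reference visit here is week 6, not week 8.
- **Analysis (Data analysis).** The index is compared between arms by independent t-tests, per side and per time point, at alpha .05.
- **Role and direction.** Swelling is a secondary outcome (Outcomes). The Hypothesis section expects that laser "will reduce pain and swelling and improve neurosensory dysfunction when compared to patients who do not receive the laser treatment".

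**The concern.** A reference length should not depend on the treatment being tested. This one is a late reading of the outcome itself, taken after all or nearly all of the treatment effect could have occurred. If some swelling remains at the reference visit and laser has reduced it, as the Hypothesis section expects, the control arm has the longer reference. More is then subtracted from control than from laser, and the contrast shrinks at the other visits.

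This does not turn on whether week 6 or week 8 is meant. That contradiction needs settling, but both visits follow treatment closely. The plan's reason for rejecting a pre-operative reference is sound, since surgery changes the length being measured. It supports any late post-operative reading, however, and applies equally at week 20, when the patient is already being seen.

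At stake is how far the swelling result can be read. A null or small contrast could reflect the reference as well as the treatment. The primary neurosensory outcome is untouched.

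**Working it through.** **The plan's own figure.** The documents give no effect, SD or power for swelling. The only figure is the general sample size: a difference of 0.5, SD 0.5 and 90% power give 22.02 per arm for a two-sided t-test, which rounds up to the stated 23. It reproduces, but says nothing about the swelling index.

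**Algebra.** Let L be the settled length, S(t) the swelling in mm at visit t, and E(t) the control-minus-laser difference in swelling. The index is

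I(t) = 100 × [S(t) − S(ref)] / [L + S(ref)].

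The control-minus-laser contrast is therefore approximately

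100 × [E(t) − E(ref)] / L,

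against a true value of 100 × E(t) / L. The loss is about 100 × E(ref) / L, the same at every visit. It is zero when E(ref) = 0.

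**Illustration.** Every input is an assumption, because the documents give none of them: L = 120 mm; control swelling 10 mm at peak, 4 mm at week 4, 3 mm at week 6 and 2 mm at week 8; laser 20% lower at every visit. The week-8 references are then 122 mm (control) and 121.6 mm (laser), so E(ref) = 0.4 mm.

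| Visit | True difference (points) | Difference shown by the index | Loss |
|---|---|---|---|
| Peak | 10/120 − 8/120 = 1.67 | 8/122 − 6.4/121.6 = 6.56 − 5.26 = 1.29 | 0.37 (22%) |
| Week 4 | 4/120 − 3.2/120 = 0.67 | 2/122 − 1.6/121.6 = 1.64 − 1.32 = 0.32 | 0.34 (52%, or 51.5% unrounded) |
| Week 6 | 3/120 − 2.4/120 = 0.50 | 1/122 − 0.8/121.6 = 0.82 − 0.66 = 0.16 | 0.34 (68%) |

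The absolute loss is nearly flat, close to 0.4/120 = 0.33 points. The percentages rise only because the assumed true difference falls.

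**Range.**

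- *1 mm left in control at week 8, same 20% effect.* Week 4 shows 3/121 − 2.4/120.8 = 0.49 against 0.67, a loss of 26%.
- *2 mm left in both arms, so the arms have converged.* Peak shows 8/122 − 6/122 = 1.64 against 1.67. Nothing is subtracted; the 1.6% change comes from the slightly longer denominator.
- *No swelling left in either arm.* The loss is zero.
- *Week 6 as the reference, with the same assumed swelling.* The references are 123 and 122.4 mm. Peak shows 7/123 − 5.6/122.4 = 5.69 − 4.58 = 1.12 against 1.67, a loss of 33%.

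**Second set of assumptions.** Take L from 100 to 140 mm, control swelling of 8 mm at visit t and 2 mm at the reference, and a laser effect of 2 mm at t. The share of the true difference retained is 98–99% if none of that effect remains at the reference visit, about 88% if a tenth remains, 72–73% if a quarter remains and about 47% if half remains.

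**The reference visit itself.** There S(t) = S(ref), so I = 0 for every patient in both arms. With no difference and no variance, the t-test cannot be informative. This needs no assumption.

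**The case against.** The strongest reply is that the harm is hypothetical. Bias needs a between-arm difference in swelling that persists to the reference visit, and no section reports residual swelling at any week. If laser acts mainly early and the arms have converged by week 8, the reference does no harm even with some swelling left. That stands, and the point has to be put conditionally.

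Three stronger readings are tempting, and the documents do not support them.

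- *That the swelling contrast is biased.* A reader might infer this from the timing alone. Timing makes the bias possible; its presence depends on data the documents do not contain.
- *That the bias grows at later visits, so that a working laser would be reported as ineffective.* The loss is about constant in mm. The large late percentages rest on assumed true differences of only 0.8 mm (week 4) and 0.6 mm (week 6). With 23 per arm and 80% power, a two-sided t-test needs a standardised difference of about 0.84. Those differences would need an SD below about 1.0 mm and 0.7 mm even with a perfect reference. The plan gives no SD for the tape, and at peak 78% of the assumed effect survives.
- *That no tape reading is planned at week 20.* The plan calls the week-8 reading the last one, which suggests this, but it schedules a week-20 evaluation without listing its contents. It is an inference.

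It is also fair to say that the outcome is secondary, and that under the trial's hypothesis the error runs against a claim of benefit. Week 8 has merits too: it is closer in time and probably more complete. These points limit the importance. They do not remove the dependence of the reference on treatment, nor the empty test at the reference visit.

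**Conclusion.** The point holds in conditional form. The swelling reference is a post-treatment reading taken no more than two weeks after the last session, and any between-arm difference still present then is subtracted from the contrast at every other visit. Where that difference runs in the same direction as the effect at the other visit, the bias is toward no effect.

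Its size cannot be taken from the documents. On the assumed values it is about 0.35 index points (0.4 mm) throughout, and it is nil if the arms have converged. The plan thus relies on convergence by the reference visit without stating or testing it. The uninformative comparison at the reference visit is certain. Since only a secondary outcome is affected, this is a cheap improvement rather than a threat to the trial's main conclusion.

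**What to change.** 1. State that the bilateral tape measurement is taken at the existing week-20 visit in both arms.
2. Name that reading as the single reference length in both places in Study Design: the baseline sentence and the index formula. This also settles the week-6 versus week-8 contradiction.
3. Pre-specify the week-8 reading as the fallback when week 20 is missing, under the same rule in both arms. A patient on the fallback has a week-8 index of zero by construction and should be left out of that visit's comparison.
4. Add a sensitivity analysis that uses the week-8 reference for all patients. Agreement between the two would show that the choice does not matter.
5. Drop the test at the reference visit. Weeks 6 and 8 then become real outcomes.

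The cost is one tape reading at a visit already scheduled, plus wording. On the downside, some patients will miss week 20, and fallback patients keep whatever bias the week-8 reference carries. Weight change by week 20 adds noise, as does growth in younger patients (Participant Recruitment puts over 30% of the surgical pool at ages 15 to 18). Randomisation should balance weight change and growth between arms.
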